5.1. Analysis Populations

As this analysis is made up from 3 cohorts of patients obtained from different studies, separate analysis populations will be defined within each cohort.

5.1.1. 205MS301-205MS303 Study Population

205MS301-303 ITT Population

Study 205MS301-303 intent-to-treat (ITT) population consists of all subjects who completed Study 205MS301 and received at least one dose of DAC HYP during the 205MS303 study, which is the population for analyses of efficacy in this cohort.

205MS301-303 Safety Population

Study 205MS301-303 safety population consists of all subjects who participated in Study 205MS301 and received at least one dose of DAC HYP treatment during the 205MS303 study. This is the population for analyses of safety in this cohort.

5.1.2. 205MS203-205MS303 Study Population

205MS203-303 ITT Population

Study 205MS203-303 intent-to-treat (ITT) population consists of all subjects who completed Study 205MS203 and received at least one dose of DAC HYP during the 205MS303 study, which is the population for analyses of efficacy in this cohort.

205MS203-303 Safety Population

Study 205MS203-303 safety population consists of all subjects who completed Study 205MS203 and received at least one dose of DAC HYP during the 205MS303 study, which is the population for analyses of safety in this cohort.

5.1.3. 205MS302-205MS303 Study Population

205MS302-303 ITT Population

Study 205MS302-303 intent-to-treat (ITT) population consists of all subjects who completed Study 205MS302 and received at least one dose of DAC HYP during the 205MS303 study, which is the population for analyses of efficacy in this cohort.

205MS302-303 Safety Population

	Protocol 205MS303 Statistical Analysis Plan	Final Version 1.0
---	--	--------------------------

Study 205MS302-303 safety population consists of all subjects who completed Study 205MS302 and received at least one dose of DAC HYP during the 205MS303 study, which is the population for analyses of safety in this cohort.

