5.2. Analysis of baseline data

The definition of baseline will be dependent on the analysis performed and the cohort of patients utilized. The following are the various definitions of baseline that may be used in the analyses:

5.2.1. 205MS301-205MS303 Study Baselines

205MS301 Baseline

Study 205MS301 Baseline is defined as the latest available value prior to or on the date of the first dose of study treatment in Study 205MS301.

205MS303 Baseline

Study 205MS303 Baseline is defined as the latest available value prior to or on the date of the first dose of study treatment in Study 205MS303.

Demographic characteristics, baseline disease characteristics and medical history will be summarized using the 205MS301-303 ITT population at the 205MS301 Baseline and at the 205MS303 Baseline.

DAC HYP Baseline

DAC HYP Baseline is equal to the 205MS301 baseline for subjects randomized to DAC HYP in 205MS301, or the 205MS303 baseline for subjects randomized to IFN β -1a in 205MS301. If no assessments, or if multiple measurements were performed on the day of first dose of DAC HYP, the last measurement prior to the first dose of DAC HYP will be used.

Unless otherwise specified, the DAC HYP Baseline will be utilized in measurements for safety assessments such as laboratory values and vital signs.

5.2.2. 205MS203-205MS303 Study Baselines

205MS303 Baseline is defined as the latest available value prior to or on the date of the first dose of study treatment in Study 205MS303.

DAC HYP Baseline

Subjects enrolled from 205MS203 study had completed the 205MS201, 205MS202, and 205MS203 studies. For subjects randomized to DAC HYP either 150 mg or 300 mg in 205MS201, the DAC HYP Baseline is defined as the 205MS201 baseline. For subjects randomized to placebo in 205MS201, the DAC HYP Baseline is defined as the 205MS202 Baseline. If no assessments, or if multiple measurements were performed on the day of first dose of DAC HYP, the last measurement prior to the first dose of DAC HYP will be used.

	Protocol 205MS303 Statistical Analysis Plan	Final Version 1.0
---	--	--------------------------

5.2.3. 205MS302-205MS303 Study Baselines

205MS303 Baseline

Study 205MS303 Baseline is defined as the latest available value prior to or on the date of the first dose of study treatment in Study 205MS303.

DAC HYP Baseline

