5.3. Key Dates Time Period Definitions

The following time periods will be defined for efficacy and safety analyses:

205MS301 Treatment Period

The 205MS301 Treatment Period is the time period as defined in the 205MS301 statistical analysis plan and includes data collected from the first dosing date to the end of treatment period visit in the 205MS301 study. For subjects who completed study treatment this is the date of the last scheduled treatment period visit in that study.

205MS303 Treatment Period refers to the time between the first dose date in 205MS303 and the date of the last available measurement prior to 180 days after the last dose date in 205MS303. This is the time period for most of the efficacy analyses and for all the safety analyses for all the populations.

Combined Study Period

For the 205MS301-303 ITT population, the Combined Study Period is the combined period of the 205MS301 and 205MS303 studies, that is the time between the first dose date in 205MS301 and the date of the last available measurement prior to 180 days after last dose date in 205MS303.

Note that for the 205MS203-303 ITT population and the 205MS302-303 ITT population, the combined study period is not necessary due to the limited number of patients in each population.

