7.2. Annualized Relapse Rate

7.2.1. Annualized Relapse Rate in the 205MS301-303 ITT Population

In Study 205MS301, relapses were defined as new or recurrent neurological symptoms not associated with fever or infection, lasting at least 24 hours, and accompanied by new objective neurological findings upon examination by the *Examining Neurologist*. In addition, these relapses must have been reviewed and confirmed by the Independent Neurology Evaluation Committee (INEC).

In Study 205MS303, relapses are defined as new or recurrent neurological symptoms not associated with fever or infection, lasting at least 24 hours, and accompanied by new objective neurological findings upon examination by the *Study Neurologist*. The subject must have objective signs on the examination confirming the event.

Therefore, Studies 205MS301 and 205MS303 utilize essentially the same definition for objective (i.e., protocol-defined) relapses, with the exception that there is no Independent Neurology Evaluation Committee (INEC) in Study 205MS303. Because relapses in 205MS303 were not evaluated by an independent committee, all investigator-confirmed relapses from 205MS301 are included whether or not independently confirmed. New or recurrent neurological symptoms that occurred less than 30 days following the onset of a protocol-defined relapse will be considered part of the same relapse (i.e., relapses with onset days ≤ 29 days of one another, will be counted as 1 relapse).

The annualized relapse rate will be summarized using the following study population and study periods:

- 205MS301-303 ITT population in the combined study period
- 205MS301-303 ITT population in the 205MS301 Treatment Period and the 205MS303 Treatment period.

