For the combined study period and the 205MS301 Treatment Period, the relapse rate will also be estimated using a negative binomial model, with adjustment for the following characteristics at the 205MS301 Baseline: baseline relapse rate (number of relapses in the 3-years prior to study entry divided by 3), history of prior IFN β use (yes/no, collected as a stratification variable in IVRS), baseline EDSS (EDSS \leq 2.5 versus EDSS $>$ 2.5) and baseline age (age \leq 35 versus age $>$ 35). The logarithmic transformation of the number of days in the study will be included in the model as the “offset” parameter. If the data are under-dispersed (assessed using the Pearson Chi-Squared statistic) or if the negative binomial model does not converge, a Poisson regression model will be used instead. The Poisson model will be adjusted for over-dispersion using a Pearson scale parameter. The treatment group is the previous treatment group of the 205MS301 study. For the 205MS303 Treatment Period, a similar analysis will be done. The adjustment will be performed with the following characteristics: number of relapses in a year prior to the first dose in 205MS303, history of prior IFN β use at the 205MS301 baseline, age (age \leq 35 versus age $>$ 35) at the 205MS303 Baseline and EDSS (EDSS \leq 2.5 versus EDSS $>$ 2.5) at the 205MS303 Baseline.

To further assess the durability of treatment, the relapse rate will also be summarized by year for the 205MS301-303 ITT population in the 205MS301 Treatment Period and the 205MS303 Treatment Period. For these analyses, rates will be tabulated by evaluating the number of relapses in each time period and the amount of follow-up time in the time period. A Poisson model will be used to estimate the relapse rate in each time period unless data are over-dispersed in which case a negative binomial model will be used.

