7.4. Sustained 6-month Disability Progression

7.4.1. Sustained 6-month Disability Progression in the 205MS301-303 ITT Population

Time to confirmed 6-month disability progression will be summarized for the following populations and study periods:

- 205MS301-303 ITT population during the 205MS303 Treatment Period, from the date of first dose in 205MS303
- 205MS301-303 ITT population during the Combined Study Period, from the date of first dose in 205MS301

Sustained disability progression is defined as: at least a 1.0 point increase on the EDSS from baseline EDSS ≥ 1.0 that is sustained for 24 weeks, or at least a 1.5 point increase on the EDSS from

	Protocol 205MS303 Statistical Analysis Plan	Final Version 1.0
---	--	--------------------------

baseline EDSS = 0 that is sustained for 24 weeks. The date of the initial visit at which the minimum increase in the EDSS is met will be the date of onset of the progression. The EDSS progression is defined as confirmed when this minimum EDSS change is present on the next study visit occurring after 158 days from the initial observation.

For the Combined Study Period, progression will be calculated relative to the EDSS score at the 205MS301 baseline. For the 205MS303 Treatment Period, progression must start after the first dose in the 205MS303 study and will be calculated relative to 205MS303 baseline.

Progression will not be confirmed at a visit where a relapse is also occurring. A subject is considered to be having a relapse for at least 29 days after the start date of a protocol-defined relapse in 205MS301 or 205MS303. If a subject meets the defined criteria of sustained progression and is also having a relapse, the subject will be required to meet the defined minimum criteria at the subsequent visit.

If a subject had a tentative progression prior to the start of alternative MS medication, the appropriate EDSS evaluation performed while taking alternative MS medication will be used to assess confirmation of the progression. Death due to MS will be counted as progression. If the subject was in the midst of a tentative progression at the time of death (e.g. the EDSS evaluation prior to death is a tentative progression), the progression date will be the tentative progression start date. Otherwise, the progression date will be the date of death. If the death was not due to MS, then the subject will be censored using the same rules as for subjects who withdraw from the study.

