8.4.3. MSFC Score

There are 3 components to the MSFC:

- (1) the average scores from the 4 trials on the 9-hole peg test (9HPT) (the 2 trials for each hand are averaged, converted to the reciprocals of the mean times for each hand and then the 2 reciprocals are averaged);
- (2) the average scores of the 2 Timed 25-Foot Walk trials;
- (3) the number correct on the Paced Auditory Serial Addition (PASAT) 3 test.

The MSFC z-score is calculated by creating z-scores for each component of the MSFC, as explained below, and averaging them to create an overall composite score, i.e.,

MSFC z-score = $(Z_{25\text{-foot-walk}} + Z_{9\text{HPT}} + Z_{\text{PASAT}3})/3$, where Z_{xxx} refers to Z-scores.

	
Protocol 205MS303 Statistical Analysis Plan
	
Final Version 1.0

---	--	--

A z-score represents the number of standard deviations a subject's test result is higher ($z > 0$) or lower ($z < 0$) than the average test result ($z = 0$) of the reference population.

Calculation for Raw and Z-score for each component

The following describes the scoring, rules for missing value imputation for each component.

Timed 25-Foot Walk Z-score Calculation

The Z-score is calculated as in the following formula:

$$Z_{25\text{-foot-walk}} = (-1) * \frac{((t_1 + t_2) / 2) - MEAN(reference)}{SD(reference)},$$

where t_1 and t_2 are the time (in seconds) from the two trials, and the mean (reference) and SD (reference) are the mean and standard deviation respectively, of baseline values for the reference population. For scores to be comparable with scores in 205MS301, the same reference population is used. Baseline values for the reference population are the values at the 205MS301 baseline for the reference population (205MS301 ITT population). The same is applicable to 9HPT and PASAT 3 Z-scores.

Timed 25-Foot Walk Raw Score Calculation

The row score is calculated as in the following formula:

$$R_{25\text{-foot-walk}} = (t_1 + t_2) / 2,$$

where t_1 and t_2 are the time (in seconds) from the two trials.

Missing Value Handling for Timed 25-Foot Walk

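### Combined Study Period analyses start at the first 205MS301 dose but keep only subjects who later rolled over, so 205MS301 losses are excluded from time zero and by-arm results lose the protection of randomisation

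*SAP*

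**What the plan says.** Section 5.1.1 sets the efficacy population for this cohort: "Study 205MS301-303 intent-to-treat (ITT) population consists of all subjects who completed Study 205MS301 and received at least one dose of DAC HYP" in 205MS303. Both conditions are met or failed only after randomisation in the parent study. Section 5.2.1 confirms that 205MS301 was randomised: "DAC HYP Baseline is equal to the 205MS301 baseline for subjects randomized to DAC HYP in 205MS301".

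Section 5.3 fixes the time origin of the Combined Study Period: "that is the time between the first dose date in 205MS301 and the date of the last available measurement", up to 180 days after the last 205MS303 dose. Three endpoints combine this origin with this set:

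- ARR, section 7.2.1: "205MS301-303 ITT population in the combined study period". The adjusted negative binomial model is by parent-study arm: "The treatment group is the previous treatment group of the 205MS301 study".
- Time to first relapse, section 7.3.1, by Kaplan-Meier and 205MS301 arm.
- Time to 6-month progression, section 7.4.1: "205MS301-303 ITT population during the Combined Study Period, from the date of first dose in 205MS301", by Kaplan-Meier and 205MS301 arm.

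The SAP plans no delayed entry, no analysis of all subjects randomised in 205MS301, and no statement of this limitation. The full parent population appears once, as the MSFC reference in section 8.4.3: "Baseline values for the reference population are the values at the 205MS301 baseline for the reference population (205MS301 ITT population".

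**The concern.** Follow-up starts two to three years before membership is decided, judging by the Week 96 and Week 144 visits of 205MS301 in section 7.6.1. Over that stretch no member of the set can withdraw or die. A subject who left 205MS301 after repeated relapses, or who completed it but took no 205MS303 dose, is absent from day one.

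Three things are at stake. First, the combined-period rates and curves describe a group that cannot be identified at its own time zero, and that group may be enriched for a benign course. Second, the arms were randomised, but the subsets that remain need not be comparable, so a contrast between early and delayed DAC HYP is observational. Third, the ITT label invites a reader to assume otherwise.

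The 205MS303 Treatment Period analyses are not affected, because there membership is settled when the clock starts.

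**Working it through.** **1. Definitions set side by side.** Membership (5.1.1) is fixed at the first 205MS303 dose, while the clock (5.3, 7.2.1, 7.3.1, 7.4.1) starts at the first 205MS301 dose. Two consequences follow without any data:

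- Section 7.3.1 prefers Kaplan-Meier because it uses the follow-up of early withdrawals. In the 205MS301 stretch there are none left to use.
- Section 7.4.1 treats a death from MS as a progression event. Such a death during 205MS301 cannot appear, because that subject cannot enter the set.

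The SAP states no figure to reproduce. It gives no number randomised, no retention by arm and no event rates in non-entrants. All values below are assumptions that show a range.

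**2. ARR over the 205MS301 stretch, closed form.** Let r be the share who enter 205MS303 and k the relapse rate of non-entrants divided by that of entrants, with equal follow-up. Then

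ARR in entrants / ARR in all treated = 1 / (r + (1 − r)k).

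Example with r = 0.70 and k = 2: 1 / (0.70 + 0.30 × 2) = 1 / 1.30 = 0.77.

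| r | k = 0.8 | k = 1 | k = 1.5 | k = 2 | k = 3 |
|---|---|---|---|---|---|
| 0.70 | 1.06 | 1.00 | 0.87 | 0.77 | 0.63 |
| 0.80 | 1.04 | 1.00 | 0.91 | 0.83 | 0.71 |
| 0.90 | 1.02 | 1.00 | 0.95 | 0.91 | 0.83 |

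**3. Arm contrast when the true rate ratio is 1.** Apply the formula to each arm and divide.

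- Arm A r = 0.70, k = 1.2: 1 / 1.06 = 0.943. Arm B r = 0.70, k = 2.0: 1 / 1.30 = 0.769. Spurious ratio A/B = 1.23.
- Arm A as above. Arm B r = 0.60, k = 2.0: 1 / 1.40 = 0.714. Ratio 1.32.
- Same r and k in both arms: ratio 1.00.

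**4. Relapse and progression, one frailty simulation.** Assumptions: gamma frailty with variance 1, a two-year parent stretch, ARR 0.30, mean progression hazard 0.06 per year, 65% retained, drop-out hazard proportional to frailty to the power g.

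| g | ARR, all → retained | 2-year progression, all → retained |
|---|---|---|
| 0 (drop-out unrelated to activity) | 0.30 → 0.30 | 10.7% → 10.7% |
| 0.5 | 0.30 → 0.24 | 10.7% → 8.7% |
| 1 | 0.30 → 0.20 | 10.7% → 7.3% |

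**5. The whole combined period.** Assumptions: true ARR 0.40 in one arm and 0.22 in the other during 205MS301, 0.22 in both arms over a 240-week extension, frailty variance 1, 205MS301 lasting 96 to 144 weeks, 10% per year background drop-out, and a 10%, 20% or 30% chance of leaving after each relapse. Figures for the 0.40 arm:

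| Chance of leaving | ARR in 205MS301, all vs roll-over | ARR combined, all vs roll-over | Relapsed by Week 96, all vs roll-over |
|---|---|---|---|
| 10% | 0.38 vs 0.33 | 0.28 vs 0.25 | 42% vs 38% |
| 20% | 0.37 vs 0.27 | 0.26 vs 0.21 | 42% vs 33% |
| 30% | 0.36 vs 0.22 | 0.25 vs 0.18 | 42% vs 29% |

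A repeat run agreed to within 0.01 on ARR and one percentage point on the proportions. The ARR gap is 0.05, 0.10 and 0.14 in the 205MS301 stretch but 0.03, 0.05 and 0.07 over the combined period, about half. With no relapse-triggered leaving, the combined ARR is 0.29 in both sets. The Week 96 arm difference falls from 13–14 points in all treated to about 12, 10–11 and 9 in roll-over subjects, so under these assumptions the selection works against DAC HYP.

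**The case against.** The strongest reply is that the direction is not established. A relapse or an EDSS progression does not stop anyone completing 205MS301. The SAP expects active subjects in the set: section 7.2.1 describes a member who took another MS drug during 205MS301, and section 7.4.1 keeps subjects who progressed there at risk in the later period. Apart from MS deaths, understatement requires non-entrants to have had more activity. This stands. A reader might infer that the results are understated as a matter of fact, and the document does not support that.

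The second reply concerns purpose. A reader might infer that the plan sets out a randomised comparison of early with delayed DAC HYP. It does not. Sections 1.1 and 1.2 define the study in parent-study completers, and section 5.4 centres efficacy on the 205MS303 period and calls the analyses generally descriptive. That section allows some hypothesis testing, but the sentence is partly redacted and proves nothing either way. A description of roll-over subjects over their whole course is a legitimate target. It still needs the right label, because the adjusted model and the curves are produced by randomised arm.

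Third, the entry conditions are printed in the definition, so the label conceals nothing from someone who reads section 5.1.1. That also stands; the risk is to readers of tables that carry only the population name.

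Finally, analysing all treated subjects does not restore a randomised long-term comparison. Later data would still come only from those who rolled over, and censoring at parent-study withdrawal may be informative: the all-treated ARR in step 5 is 0.36 to 0.38 against a true 0.40. This is why the new analysis belongs beside the planned one and should not replace it.

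**Conclusion.** The structural fault is certain from the text: the set is chosen on later events, the clock starts before them, 205MS301 losses are deleted instead of censored, and MS deaths in that stretch are excluded by definition. The by-arm combined-period results are therefore non-randomised.

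The numerical effect is conditional. Understatement is likely if those lost had more disease activity, near zero if drop-out was unrelated to activity, and reversed if they had less. With 70% to 90% retained and k from 0.8 to 3, the ARR over the 205MS301 stretch would be 0.63 to 1.06 of its all-treated value, and the combined-period effect is smaller. The arm contrast can shift in either direction, depending on which arm lost more active subjects. None of these inputs is in the SAP.

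Because the analyses are mainly descriptive and no confirmatory arm test is named, this should be fixed as a cheap improvement. It is not a fault that invalidates the plan.

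**What to change.** - For the Combined Study Period, add an analysis of ARR, time to first relapse and time to 6-month progression in all subjects randomised and dosed in 205MS301, by randomised arm. Non-entrants contribute their 205MS301 events and are censored at their last 205MS301 assessment. Keep the existing relapse, progression and alternative-medication rules, including the use of investigator-confirmed 205MS301 relapses. Report it beside the roll-over result.
- Rename the current set the roll-over population and mark its by-arm combined-period results as non-randomised.
- Tabulate non-entrants by arm, with their 205MS301 relapse and progression outcomes, so that a reader can judge the direction.
- State as limitations that data after 205MS301 come only from roll-over subjects and that censoring at parent-study withdrawal may be informative.
- Leave the 205MS303 Treatment Period analyses as they are.

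The cost is SAP wording, one extra table and a rerun of existing programs. The parent data should already be held, since section 8.4.3 draws on the 205MS301 ITT population. The price is that long-term figures may look less favourable and parent-study drop-outs are censored early.

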5.2. Analysis of baseline data

The definition of baseline will be dependent on the analysis performed and the cohort of patients utilized. The following are the various definitions of baseline that may be used in the analyses:

5.2.1. 205MS301-205MS303 Study Baselines

205MS301 Baseline

Study 205MS301 Baseline is defined as the latest available value prior to or on the date of the first dose of study treatment in Study 205MS301.

205MS303 Baseline

Study 205MS303 Baseline is defined as the latest available value prior to or on the date of the first dose of study treatment in Study 205MS303.

Demographic characteristics, baseline disease characteristics and medical history will be summarized using the 205MS301-303 ITT population at the 205MS301 Baseline and at the 205MS303 Baseline.

DAC HYP Baseline

DAC HYP Baseline is equal to the 205MS301 baseline for subjects randomized to DAC HYP in 205MS301, or the 205MS303 baseline for subjects randomized to IFN β -1a in 205MS301. If no assessments, or if multiple measurements were performed on the day of first dose of DAC HYP, the last measurement prior to the first dose of DAC HYP will be used.

Unless otherwise specified, the DAC HYP Baseline will be utilized in measurements for safety assessments such as laboratory values and vital signs.

5.2.2. 205MS203-205MS303 Study Baselines

205MS303 Baseline is defined as the latest available value prior to or on the date of the first dose of study treatment in Study 205MS303.

DAC HYP Baseline

Subjects enrolled from 205MS203 study had completed the 205MS201, 205MS202, and 205MS203 studies. For subjects randomized to DAC HYP either 150 mg or 300 mg in 205MS201, the DAC HYP Baseline is defined as the 205MS201 baseline. For subjects randomized to placebo in 205MS201, the DAC HYP Baseline is defined as the 205MS202 Baseline. If no assessments, or if multiple measurements were performed on the day of first dose of DAC HYP, the last measurement prior to the first dose of DAC HYP will be used.

	Protocol 205MS303 Statistical Analysis Plan	Final Version 1.0
---	--	--------------------------

5.2.3. 205MS302-205MS303 Study Baselines

205MS303 Baseline

Study 205MS303 Baseline is defined as the latest available value prior to or on the date of the first dose of study treatment in Study 205MS303.

DAC HYP Baseline

DAC HYP Baseline is equal to the 205MS302 baseline for all subjects in the 205MS302-303 safety population. If no assessments, or if multiple measurements were performed on the day of first dose of DAC HYP, the last measurement prior to the first dose of DAC HYP will be used.

